TITLE

Electric Blower Based Ventilator Used During Procedural Sedation

NCT NUMBER

NCT02621463

DOCUMENT DATE

September 30, 2015 (date of the most recent approval of the IRB application from which the Study Protocol was extracted)

STUDY PROTOCOL (extracted from IRB_00074281, approved on Sep 30, 2015)

All study procedures will be performed in adult patients following informed consent at the endoscopy suite of the University of Utah Health Sciences Center in Salt Lake City, Utah. A ventilation mask will be placed on the patient's face and connected to the V60 ventilator. Supplemental oxygen will be delivered by the V60 ventilator through the mask; the concentration of oxygen delivered will be left to the clinician's discretion. A modified mask with multiple small leaks will be used with a standard elastomeric H-strap to secure it to the patient's face.

The endoscopy suite nurse and technicians will attach all clinically necessary standard sensors and connect them to the patient and monitoring system. Height, weight, and neck circumference will be measured and recorded digitally on an encrypted laptop. In addition to the standard of care monitors, we will collect data from additional non-invasive modalities and save the data to a laptop using custom software for later analysis. Respiratory Inductance Plethysmography bands (Q-RIP, Braebon, Kanata, Canada) (also called chest bands) will be placed to monitor the patients' tidal volumes. The chest bands will be calibrated using data from a tight fitting mask connected to a flow sensor collected for approximately 1-3 minutes at the end of the case. The concentration of oxygen delivered will be left to the clinician's discretion and will be recorded to a data sheet.

Pressure and flow sensors included in the V60 ventilator will be used to monitor the patients' tidal volumes and respiratory rate during the procedure. The data that will be collected and recorded on the laptop will include: RIP data, mask pressure, flow, and breath rate. An additional flow sensor connected to an NM3 (LoFlo/NM3, Philips Medical) will be placed in line with the V60 ventilator. The additional flow sensor is an approved medical device for measuring flow in patients receiving respiratory support and will have no effect on the functionality of the V60 ventilator or its ability to provide patient support and monitoring. It simply collects additional data that will be used to demonstrate the accuracy of our prototype system's algorithm.

The ventilator mask will be placed on the patient's face according to their comfort using an elastomeric H-strap. CPAP of 8 cm H₂O will be the starting setting for the V60 ventilator. The clinician will determine the concentration of oxygen that shall be delivered to the patient. The V60 ventilator is capable of providing concentrations between 21% - 100% of oxygen. Unless otherwise directed by the clinician, the V60's default setting of 40% will be used.

The clinical procedure and administration of sedation medication other than the ventilatory support and monitoring will follow the clinical routine used for colonoscopies. The attending staff will be instructed to not alter medication doses or any other standard of care just because of the study or use of the ventilator. An anesthesiologist will be immediately available for consult and assistance during all patient treatment.

STATISTICAL ANALYSIS

All statistical analysis was performed using Excel (Microsoft, 2013) and R version 3.3.1 (2016-06-21). Demographic data were analyzed using the Welch two sample t-test to show demographic uniformity across both populations. p values for the primary and secondary outcome variables were calculated using

Mann-Whitney test due to nonparametric data and the uneven sample sizes between the intervention group and the control group. SpO₂ data were averaged over 15 data points (15 s) to eliminate artifacts in the data due to movement and disconnection of the sensor from the patient. Area-under-curve (AUC) analysis integrated the difference between the SpO₂ data and the 90% threshold every second. A sample size of 29 patients was calculated to have a 90% power to detect a 9% difference in means of the percent time of the procedure that the patient experienced apnea. We expected to show that the use of CPAP during procedural sedation would reduce apneic time from these procedures and yield an average of less than 2% of the procedure time in an apneic state.

(extracted from: Fogarty M, Orr JA, Sakata D, Brewer L, Johnson K, Fang JC, Kuck K. A comparison of ventilation with a non-invasive ventilator versus standard O₂ with a nasal cannula for colonoscopy with moderate sedation using propofol. J Clin Monit Comput. 2020 Dec;34(6):1215-1221)

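### The 15-s mean dilutes SpO₂ artifacts rather than eliminating them, so the area below 90% can keep sensor artifact and lose part of short real dips

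*Combined protocol and SAP*

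**What the plan says.** The Statistical Analysis section gives one rule for cleaning the SpO₂ signal. The data were "averaged over 15 data points (15 s) to eliminate artifacts in the data due to movement and disconnection of the sensor". The next sentence defines the outcome: "Area-under-curve (AUC) analysis integrated the difference between the SpO₂ data and the 90% threshold every second". Fifteen points in 15 s means one sample per second.

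Neither the Study Protocol text nor the Statistical Analysis section gives a signal-validity flag, a plausible range, a rule for sensor-off periods or an analysis of unsmoothed data. They also leave open:

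- how a disconnected sample is stored;
- whether the mean is running or in blocks;
- whether the averaged series is the one integrated;
- whether only values below 90% count.

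Outcomes were compared with the "Mann-Whitney test due to nonparametric data and the uneven sample sizes between the intervention group and the control group". The sample size rests on a different quantity: "a 9% difference in means of the percent time of the procedure that the patient experienced apnea".

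**The concern.** The plan recognises that movement and disconnection contaminate the SpO₂ signal, and it relies on a mean alone to remove them. A mean is linear, so a bad sample is diluted but not discarded. Whether the diluted artifact still counts depends on its depth, its length and how far the baseline lies above 90%. The same smoothing pulls short real desaturations up towards the threshold.

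At stake is what the SpO₂ area measures. A patient with no true desaturation can receive a positive area from the sensor, and a patient with a short real dip can receive too little or none.

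**Working it through.** **Inputs.** From the Statistical Analysis section: a 15-point window, 1 s per point, a 90% threshold and a 1-s integration step. Assumed, because the documents give no SpO₂ values: a baseline of 97% (range 95–99%), the artifact levels and durations below, a running mean, the averaged series integrated, and only values below 90% counted. The plan states no SpO₂ figure to reproduce, and the 29 patients are not an input here.

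**Formula.** Take a step from baseline B to level L lasting k seconds (k ≤ 15). A window holding j bad samples has mean B − (B − L)·j/15. Each j from 1 to k − 1 occurs in 2 windows, and j = k occurs in 16 − k windows. Each window adds max(0, (B − L)·j/15 − (B − 90)) to the area. The artifact vanishes only if (B − L)·k/15 ≤ B − 90.

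**70% for 5 s, B = 97.** Raw area: 5 × 20 = 100 %·s. Each bad sample lowers the mean by 27/15 = 1.8 points, and the margin is 7.
- j ≤ 3: at most 5.4, so nothing is counted.
- j = 4: 7.2 − 7 = 0.2, in 2 windows = 0.4.
- j = 5: 9.0 − 7 = 2.0, in 11 windows = 22.0.
- Total left: 22.4 %·s (40 at a 95% baseline, 7 at 99%).

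**Zeros for 3 s, B = 97.** Raw area: 3 × 90 = 270 %·s. Each zero lowers the mean by 97/15 = 6.467 points.
- j = 1: below the margin, so nothing is counted.
- j = 2: 12.933 − 7 = 5.933, in 2 windows = 11.9.
- j = 3: 19.4 − 7 = 12.4, in 13 windows = 161.2.
- Total left: 173 %·s (200 at 95%, 149 at 99%).
- If the samples are stored as missing and skipped: 0.

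**Where removal stops.** False area first appears at the first whole second above 15 × (B − 90)/(B − L). At B = 97:
- zeros: 15 × 7/97 = 1.08, so 2 s;
- 70%: 15 × 7/27 = 3.89, so 4 s;
- 80%: 15 × 7/17 = 6.18, so 7 s.

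Thus 70% for 3 s, or a single 1-s zero, is fully removed at this baseline. At 95% the single zero leaves 20 %·s.

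**Real dips.** For a V-shaped fall from 97% to 85% and back, the 15-s mean at the bottom is 85 + slope × 56/15. Here 56 is the sum of the distances from the centre, −7 to +7.

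| Each way | Lowest 15-s mean | Raw area (%·s) | After mean (%·s) | Kept (baselines 95–99%) |
|---|---|---|---|---|
| 15 s | 85 + 0.8 × 56/15 = 87.99 | 31.4 | 16.5 | 52% (67–37%) |
| 30 s | 85 + 0.4 × 56/15 = 86.49 | 62.6 | 55.1 | 88% (92–84%) |
| 60 s | 85 + 0.2 × 56/15 = 85.75 | 125.0 | 121.3 | 97% (98–96%) |

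**Other readings of the unstated points.**
- Block mean: 3-s zeros leave 89–186 and 70% for 5 s leaves 0–30, depending on block alignment.
- Unaveraged series integrated: 270 and 100 remain in full, and real dips are not blunted.
- Signed difference integrated: 3-s zeros shift the total by 3 × (−97) = −291 %·s with or without averaging, so artifacts stay in full and real dips are not blunted.

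**The case against.** The strongest reply is that the practical size depends on facts that the documents do not state. The largest figures need disconnection to be stored as zeros. If it is stored as missing and skipped, that part is nil. This stands. Using averaging against disconnection suggests that such samples entered as values, but does not prove it. The text is also a short extract from a journal article, so the absence of another cleaning step here does not show that none was applied.

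Second, a reader might infer that averaging manufactures false desaturation. It does not. The function max(0, 90 − x) is convex, so averaging can only keep or lower the area; in the examples 270 falls to 173 and 100 to 22. The residue was already in the raw data. Its spread over more seconds does not matter for an area.

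Third, a reader might infer a biased treatment comparison. The documents do not support that. They give no artifact rate, show no difference in sensor disturbance between groups, and do not say whether the SpO₂ area is a primary or secondary outcome. If it is tested by Mann-Whitney, values enter as ranks, so one huge area counts no more than any other top rank. Ranks can still move when a true zero becomes positive or a real short dip becomes zero.

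Fourth, the apnea calculation might seem to be affected. Apnea time is not stated to come from SpO₂, so the sample size is outside this point.

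What the reply does not remove is that the one stated cleaning rule falls short of its stated purpose.

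**Conclusion.** The concern holds in a limited form. The 15-s mean reduces movement and disconnection artifacts but does not eliminate them, and it costs some area in short real desaturations. On the natural reading and at baselines of 95–99%, the two example artifacts leave 7–40 %·s (70% for 5 s) and 149–200 %·s (3 s of zeros, only if zeros are stored). The loss of real area is material for dips of about 15 s each way and small by 60 s.

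These figures rest on assumed baselines, artifact shapes and a running mean. That a mean only dilutes bad samples does not depend on those assumptions. The size and direction of any effect on the group comparison cannot be determined from the documents. The change should be made, but nothing here shows that the trial's conclusion is wrong.

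**What to change.** **Main analysis.** Before any averaging, set to missing every sample that is flagged sensor-off, is zero, or lies outside a prespecified plausible range. Fix the limits without reference to group, run identical code in both groups, and leave the masked seconds out of the area. Report percent valid time by group. State how disconnected samples are stored, the window type, the series integrated, and that only values below 90% count.

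**Sensitivity analysis.** Report the area below 90% on masked, unsmoothed data, to show how much the smoothing blunts short dips.

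**Wording.** Say that the averaging reduces artifacts, and that movement artifacts with plausible values remain.

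**What this does and does not mend.** With an assumed lower limit of 50%, zeros of 1–10 s leave 0. A false 70% for 5 s passes the range check and still leaves 22.4 %·s after mask and mean, and 100 %·s on masked, unsmoothed data. The main analysis still blunts short real dips. A dropout inside a real dip loses real area. For a 10-s zero at the bottom of a fall to 85% (30 s each way, true area 62.6 %·s), masked unsmoothed data keep 22.6 and mask-then-mean keeps 11.4, against 915 with the mean alone. This is why valid time must be reported.

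**Cost.** A few lines of code, a re-run of an analysis that the section describes as done, and slightly less analysable time: 10 s masked in an assumed 1,200-s procedure is 10/1,200 = 0.8%. It requires stored 1-Hz SpO₂ values for both groups. That must be checked first, because the Study Protocol's list names neither SpO₂ nor a sensor-off flag: "The data that will be collected and recorded on the laptop will include: RIP data, mask pressure, flow, and breath rate". If those values were not kept, the limitation should be stated with the SpO₂ result.
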